4.3.2.5 Subgroup analyses

Subgroups analysis and description of missing data will be summarized using methods similar to those of TKV, except that eGFR (CKD-EPI equation) at screening will be (45 to <60, 60 to <75, 75 to <90) (see Section 4.3.1.5).

4.4 SECONDARY ENDPOINT(S) ANALYSIS

4.4.1 Stage 1 key/confirmatory secondary endpoint(s)

4.4.1.1 Definition of endpoint(s)

In Stage 1, the following endpoints are defined as key secondary endpoints:

- Annualized rate of change in eGFR (CKD-EPI equation) from baseline to 18 months.
- Change in pain from baseline to 18 months. Pain score will be based on BPI Item 3, assessed from the daily symptom diary.
- Change in fatigue from baseline to 18 months. Fatigue score will be based on BFI Item 3, assessed from the daily symptom diary.

4.4.1.2 Main analytical approach

The analysis of eGFR in Stage 1 will be identical to those of Stage 2 (see Section 4.3.2.2).

Daily diaries scores will be averaged over 7 consecutive assessments prior to the baseline, Month 3 and Month 12 visit and over the 14 consecutive days prior to the planned Month 18 visit. At least 50% of the days in the observation period (ie, 4 or more of the 7 days for baseline, Month 3 and Month 12; 7 or more of the 14 days for Month 18) are required to calculate the average score on non-missing data (4, 5).

Change in pain and change in fatigue from baseline to 18 months will be analyzed on the ITT population, regardless of whether or not participants completed the treatment period, using a mixed effect model with repeated measures (MMRM). The model will include the fixed categorical effects of treatment (venglustat 15 mg, venglustat 8 mg or placebo), Mayo Imaging Classification (as per randomization stratification factor: Class 1C versus 1D versus 1E), time point (Month 3, Month 12, Month 18), treatment-by-time point interaction, randomization strataby-time point interaction as well as the continuous fixed covariates of baseline and the baseline-by-time point interaction.

This model will be run using SAS Mixed procedure with an unstructured correlation matrix to model the within-patient errors. Parameters will be estimated using restricted maximum likelihood method. Denominator degrees of freedom will be estimated using Kenward-Roger approximation. This model will provide baseline adjusted least-squares means estimates at Month 18 for each study intervention groups with their corresponding standard errors (SEs) and 95% confidence intervals (CI). Within group mean change in pain will be obtained from the MMRM, using weights for each stratum (Mayo Class 1C, 1D and 1E) equal to the overall proportion of participants in each stratum in the Stage 1 ITT population (ie, "population weight"). Population weights are considered more appropriate than equal coefficients due to expected unbalances in the study population between levels of the randomization stratification factors.

Overall effect of venglustat will be assessed using a Multiple Comparison Procedure similar to those of the primary endpoint (see Section 4.3.1.2). In addition, p values for the comparison of each dose of venglustat versus placebo will be presented for descriptive purpose.

There will be no imputation of missing data.

In the case of the model does not converge due to high number of missing data, only descriptive summaries by visits will be provided.

4.4.2 Combined Stage 1 and Stage 2 key/confirmatory secondary endpoint(s)

4.4.2.1 Definition of endpoint(s)

In combined Stage 1 and Stage 2, the following endpoints are defined as key secondary endpoints:

- Annualized rate of change in TKV from baseline to 18 months
- Change in pain from baseline to 24 months, based on BPI Item 3 assessed from the daily symptom diary
- Change in fatigue pain from baseline to 24 months, based on BFI Item 3 assessed from the daily symptom diary

4.4.2.2 Main analytical approach

As no post-baseline MRI data will be available in Stage 2 at the time of the study discontinuation the analysis of TKV in Combined Stage 1 and Stage 2 will not be done.

Change in pain and change in fatigue from baseline to 24 months will be analyzed using an MMRM similar to the one used in Stage 1, except the time point will include Month 3, Month 12, Month 18 and Month 24 (see Section 4.4.1.2).

In the case of the model does not converge due to high number of missing data, only descriptive summaries by visits will be provided.

4.4.3 Supportive secondary endpoint(s)

Other safety secondary endpoints will be defined in Section 4.7.3.

- Change in BDI-II score during the treatment emergent period (Section 4.7.3.5)
- Change in the lens clarity by ophthalmological examination during the treatment emergent period (Section 4.7.3.4)

4.5 TERTIARY/EXPLORATORY ENDPOINT(S) ANALYSIS

4.5.1 Definition of endpoint(s)

In Stage 1 and Stage 2, the following endpoints are defined as exploratory efficacy endpoints:

- Annualized rate of change in TLV based on MRI from baseline to 18 months on participants with htTLV >1 L/m
- Change in:
 - Urine osmolality from baseline to 18 months in Stage 1 and 24 months in combined Stage 1 and Stage 2 (in participants not on diuretic at baseline)
 - Nocturia from baseline to 18 months in Stage 1 and 24 months in combined Stage 1 and Stage 2, based on the daily symptom diary (see Section 4.8.3)
 - Systolic BP during the treatment emergent period (see Section 4.7.3.1)
 - Diastolic BP during the treatment emergent period (see Section 4.7.3.1)
 - Biomarkers associated with ADPKD (eg, FGF23 and ADMA) from baseline to 18 months from baseline to 18 months in Stage 1 and 24 months in combined Stage 1 and Stage 2 (see Section 4.8.4)
 - Pain (BPI), fatigue (BFI) and health status (EQ-5D-5L) from baseline to 18 months in Stage 1 and 24 months in combined Stage 1 and Stage 2 (see Section 4.8.3)
 - Glucosylceramide (GL1) and GM3 from baseline to 18 months in Stage 1 and 24 months in combined Stage 1 and Stage 2 (see Section 4.8.2)
- Type, frequency, and dosage of analgesic/over the counter (OTC) pain medication administration from baseline to 24 months (see Section 4.8.3)
- Rate of all-cause hospitalization (see Section 4.8.5)

4.5.2 Main analytical approach

As no post-baseline MRI data will be available in Stage 2 at the time of the study discontinuation the analysis of TLV in Combined Stage 1 and Stage 2 ITT population will not be done.

For other quantitative exploratory endpoints only descriptive summaries by visits will be provided.

The urine osmolality will be analyzed using the average of the 3 separate measurements performed between visit date - 3 and visit date + 1 at each planned visit performed within analysis time windows (see Table 12):

- first spot at visit day-2 am
- second spot the day of visit am
- third spot from the 24-hour urine sample, if any, else sample at the time of visit

All participants on oral diuretic medications at the time of the 1st IMP administration (ie, start date of medication prior to the 1st administration of IMP and end of medication after the 1st administration of IMP or missing) will be excluded from the urine osmolality analysis.

Analyses of pain medications and hospitalization will be defined in Section 4.8.3 and Section 4.8.5.

4.6 MULTIPLICITY ISSUES

A weighted Bonferroni-based closed test procedure will be used in order to control the Type I error rate for the entire study. This procedure will handle both multiplicity of endpoints (primary and secondary endpoints) and multiplicity of analysis (analysis at end of Stage 1 and analysis at end of Stage 2). Multiplicity of doses will be handled using the Multiple Comparison Procedure described in Section 4.3.1.2.

The statistical procedure is illustrated using a graphical approach (6) and is shown in Figure 2. This procedure will ensure a strong control of the overall Type-I error rate at the 0.05 level for the entire study.

No further adjustments will be made for supplementary analyses or analyses of other secondary efficacy endpoints, for which p-values will be provided for descriptive purpose only. In addition, p-values for the comparison of each dose of venglustat versus placebo will be presented for descriptive purpose.

Analysis at Analysis at end of Stage 1 end of Stage 2 α = 0.04 α = 0.01 TKV growth rate 0.975 eGFR rate of decline **Primary endpoint** End of stage 1 End of stage 2 0.025 1 eGFR rate of decline TKV growth rate **Secondary endpoints** End of stage 2 End of stage 1 1 1 Change in pain Change in pain End of stage 1 End of stage 2 1 1 Change in fatigue Change in fatigue End of stage 1 End of stage 2

Figure 2 - Graphical illustration of the procedure for handling multiplicity

4.7 SAFETY ANALYSES

All safety analyses will be performed on the Extended combined Stage 1 and Stage 2 safety population as defined in Section 3, unless otherwise specified, using the following common rules:

- The analysis of the safety variables will be essentially descriptive, and no testing is planned.
- Safety data in participants who do not belong to the safety population (eg, exposed but not randomized will be provided separately if any.

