SAP Version	Approval Date	Changes	Rationale
		The two-step analysis is not applicable anymore and replaced by a single analysis of all data available on combined Stage 1 & Stage 2 analysis (see Section 1.1 and Section 4.9.3)	Following decision to discontinue EFC15392 and LTS15823 studies based on EFC15392 futility analysis
		Efficacy analyses on Stage 1 ITT population and combined Stage 1 and Stage2 population will be conducted on all data available up to database lock (see Section 4.1, Section 4.3.1). No multiple imputation will be done, only analysis on observed data will be performed (see Section 1.2.1, Section 4.3.1.1, Section 4.3.1.2, and Section 4.3.2.2).	
		As no post-baseline MRI data will be available in Stage 2 at the time of the study discontinuation, the analysis of TKV and TLV in Combined Stage 1 and Stage 2 will not be done (see Section 1.2.1, Section 4.4.2.2 & Section 4.5.2).	
		Secondary analysis of eGFR on all randomized participants will be replaced by descriptive summary across visit on the secondary Stage2 ITT population (see Section 3 and Section 4.3.2.4)	
		For all tertiary endpoints, due to the high number of missing data at month18 and month24, MMRM will be replaced by only descriptive summary by visits (see Section 4.5.2, Section 4.8.2, Section 4.8.3 and Section 4.8.4). For the secondary endpoints (BPI-Item3 & BFI Item3), in case the MMRM does not converge due to high number of missing data, then only descriptive summary by visits will be provided (see Section 4.4.1.2 and Section 4.4.2.2)	
		As no GM3 sample tested at the time of the study discontinuation, the analysis of GM3 will not be done (see Section 4.8.2)	
		Safety populations and all safety analyses on Stage 1 populations are removed. All safety analyses will be performed on the extended combined Stage 1 and Stage 2 safety population, including all participants with an eGFR between 30 and 89.9 mL/min/1.73 m ² at screening (see Section 3 and Section 4.7).	
		mGFR analysis has been removed as no data available (see Section 4.5.1).	

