1 INTRODUCTION

1.1 STUDY DESIGN

This is an international, multicenter, randomized, double-blind, placebo-controlled, two-stage study in adult participants at risk of rapidly progressive Autosomal Dominant Polycystic Kidney Disease (ADPKD) aged 18 to 50 years in Stages 1 and 2. In addition, Stage 2 also includes participants aged 18 to 55 years with a screening estimated Glomerular Filtration Rate (eGFR) between 30 and 44.9 mL/min/1.73 m².

The study is divided into 2 stages:

Stage 1: an up to 30-days screening period including a 2-week placebo run-in (to identify participants who are unlikely to follow the assigned treatment regimen), followed by a randomized, double-blind, comparative placebo-controlled core treatment period of 24 months duration.

After run-in, eligible participants, aged 18 to 50 years with an eGFR in (45 to 89.9) are randomized with a 1:1:1 ratio to placebo, 8 mg venglustat, or 15 mg venglustat.

Participants are stratified based on their predicted ADPKD progression rate (1C versus 1D versus 1E) according to Mayo Imaging Classification and geographical region (North America, Europe, China, Republic of Korea, Rest of the World).

After the interim unblinded aggregate safety review by the DMC of the first 150 randomized participants from Stage 1 having completed at least 1 month of treatment (or have prematurely discontinued), the DMC determined that the 15 mg dose was the highest dose to be safe and well tolerated in Stage 1, and recommended the venglustat 15 mg dose for Stage 2.

Stage 2: starts with an up to 30-day screening period including a 2-week placebo run-in (to identify participants who are unlikely to follow the assigned treatment regimen), followed by a randomized, double-blind, comparative core treatment period of 24 months duration. After run-in, eligible participants aged 18 to 55 years with an eGFR of 30 to 89.9 are randomized with a 1:1 ratio to placebo and 15 mg venglustat. Participants are stratified based on their predicted progression rate (1C versus 1D versus 1E) according to Mayo Imaging Classification and geographical region (North America, Europe, China, Republic of Korea, Rest of the World).

Participants who completed 24 months of treatment in EFC15392 study may be given the option to enroll into an open-label long-term extension study LTS15823 (additional 24 months of treatment with 15 mg venglustat).

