3 ANALYSIS POPULATIONS

The following populations for analyses are defined:

Table 4 - Populations for analyses

Population	Description
Screened	All participants who signed the Informed Consent Form (ICF).
Randomized	All participants from screened population who have been allocated to a randomized intervention by Interactive Response Technology (IRT) regardless of whether the intervention was received or not.
Exposed	All screened participants who took at least 1 dose of study intervention.
Population without trial impact (disruption) due to COVID-19	All randomized participants without any critical or major deviation related to COVID19 and who did not permanently discontinue treatment due to COVID19 and who did not permanently discontinue study due to COVID19
Stage 1 Intent-to-treat (ITT)	All participants randomized in Stage 1.
	Participants will be analyzed according to the intervention allocated by randomization (venglustat 15 mg, venglustat 8 mg or placebo).
Stage 1 Pharmacokinetic (PK)	All participants randomized in Stage 1 who took at least 1 dose of study intervention and who have at least one post-baseline PK assessment. Participants will be analyzed according to the intervention they actually received.
Stage 1 Pharmacodynamic (PD)	All participants randomized in Stage 1 who took at least 1 dose of study intervention and who have at least one post-baseline PD assessment. Participants will be analyzed according to the intervention they actually received.
Combined Stage 1 and Stage 2 ITT	All participants with an eGFR between 45 and 89.9 mL/min/1.73 m ² at screening who are randomized in Stage 1 or Stage 2.
	Participants will be analyzed according to the intervention allocated by randomization (venglustat 15 mg, venglustat 8 mg or placebo).
Secondary Stage 2 ITT	All participants with an eGFR between 30 and 44.9 mL/min/1.73 m ² at screening who are randomized in Stage 2. Participants will be analyzed according to the intervention allocated by randomization (venglustat 15 mg or placebo).
Extended Combined Stage 1 and Stage 2 Safety	All participants with an eGFR between 30 and 89.9 mL/min/1.73 m ² at screening who are randomized in Stage 1 or Stage 2 and who took at least 1 dose of study intervention. Participants will be analyzed according to the intervention they actually received.

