4 STATISTICAL ANALYSES

4.1 GENERAL CONSIDERATIONS

In general, continuous data will be summarized using the number of observations available, mean, standard deviation (SD), median, [Q1, Q3] minimum, and maximum. Categorical and ordinal data will be summarized using the count and percentage of participants.

The baseline value is defined as the last available value before or equal to the first dose of double-blind investigational medicinal product (IMP). For participants randomized but not exposed, the baseline value is defined as the last available value before or equal to the date and time of randomization.

Baseline eGFR is defined for each participant as the average of eGFR values assessed prior or equal to first IMP, or randomization for participants randomized and not exposed.

Baseline of patient daily diaries scores is defined for each participant as the average of the assessments during the 7 days prior the 1st IMP or prior randomization for participants randomized and not exposed.

Baseline of urine osmolality is defined as the average of the 3 separate assessments within the 3 days prior or equal to the baseline visit (Visit 3).

Primary efficacy analyses will be conducted on Stage 1 ITT population and on combined Stage 1 and Stage 2 ITT populations (see Section 3), including all data available at the time of database lock from baseline to Month 24:

• Participants from Stage 2 with an eGFR between 30 and 44.9 mL/min/1.73 m² at screening will not be included in the primary efficacy analysis. A supplemental descriptive efficacy analysis on these participants will be performed separately (see Section 3 and Section 4.3.2.4).

Safety analyses will be conducted in the extended combined Stage 1 and Stage 2 population (see Section 3) including all data available from baseline to the end of the 24-month double-blind treatment period. Unless otherwise specified, analyses will be performed by intervention group (and overall for baseline and demographics characteristics).

Observation period

The observation period will be divided into 4 segments:

- The **pre-treatment period** is defined as the period up to first IMP administration.
- The **treatment-emergent** (TE) **period** is defined as the period from the first IMP administration up to the last IMP administration in EFC15392 study +30 days or up to the first visit in LTS15823 study, whichever comes earlier. The treatment-emergent period includes the following 2 periods:

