The AE summaries of Table 7 will be generated with number (%) of participants experiencing at least one event. The all TEAE summary by Primary SOC and PT (and other safety summaries (eg, SAEs, deaths), if deemed needed after TEAE evaluation) will be performed by trial impact (disruption) due to Covid-19.

Table 7 - Analyses of adverse events

Type of AE	MedDRA levels
All TEAE	Primary SOC, HGLT, HLT and PT
	Primary SOC and PT
Common TEAE (>5% in any group)	Primary SOC and PT
TEAE related to IMP as per Investigator's judgment	Primary SOC and PT
TEAE by maximal intensity	Primary SOC and PT
Treatment emergent SAE	Primary SOC and PT
Treatment emergent AESI	Primary SOC and PT
TEAE leading to permanent intervention discontinuation	Primary SOC and PT
TEAE leading to death (death as an outcome of the AE as reported by the Investigator in the AE page)	Primary SOC and PT
Treatment emergent Covid-19 related AE	Primary SOC and PT

b The table of all TEAEs presented by SOC and PT will define the presentation order for all other tables (eg, treatment-emergent SAE) presented by SOC and PT, unless otherwise specified.

Type of AE	MedDRA levels	
Pretreatment AE	Overview ^a	_
Pretreatment AESI	Primary SOC and PT	
Post-treatment AE	Overview ^a	

a Will include the following AE categories: any AEs, any serious AEs, any AESIs any AEs leading to death, any AEs leading to permanent intervention discontinuation

Analysis of deaths

In addition to the analyses of deaths included in Table 7 the number (%) of participants in the following categories will be provided:

- Deaths during the treatment-emergent and post-treatment periods by reason for death
- Deaths in non-randomized participants or randomized but not exposed participants

Analysis of adverse events of special interest (AESIs)

Adverse events of special interest (AESIs) and other AEs of interest will be selected for analyses as indicated in Table 8. Number (%) of participants experiencing at least one event will be provided for each event of interest. Tables will be sorted as indicated in Table 6.

Table 8 - Selections for AESIs

AESIs and other AEs of interest	Selection
Pregnancy of a female subject or female partner of a male subject	e-CRF specific pregnancy page
Symptomatic overdose (serious or non- serious) with IMP	e-CRF specific symptomatic overdose page
Increase in alanine transaminase (ALT)	e-CRF specific AESI tick box on the AE page

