4.7.3 Additional safety assessments

4.7.3.1 Laboratory variables, vital signs and electrocardiograms (ECGs)

The following laboratory variables, vital signs and electrocardiogram (ECG) variables will be analyzed. They will be converted into standard international units.

- Hematology:
 - Red blood cells and platelets and coagulation: hemoglobin, hematocrit, erythrocyte count, platelet count, prothrombin time (PT), prothrombin international normalized ratio (INR), activated partial thromboplastin time (aPTT).

- White blood cells: white blood cell count, neutrophils, lymphocytes, monocytes, basophils, eosinophils.
- Clinical chemistry:
 - Metabolism: glucose, protein, albumin.
 - Electrolytes: sodium, potassium, chloride, bicarbonate, calcium.
 - Renal function: creatinine, blood urea nitrogen, serum cystatin C.
 - Liver function: alanine aminotransferase, aspartate aminotransferase, alkaline phosphatase, gamma glutamyl transferase, total and direct bilirubin.
 - Pregnancy test: Serum β-human chorionic gonadotropin (all female participants).
- Urinalysis:
 - Urinalysis for quantitative analysis: pH, specific gravity, proteins, and glucose.
- Vital signs: heart rate, systolic and diastolic blood pressure, weight.
 - For all seated BP measurements, SBP and DBP will be analyzed using the average of the 3 to 5 separate measurements at each visit.
- ECG variables: heart rate, PR, QRS, QT, and corrected QTc (according to Bazett/Fridericia).

Data below the lower limit of quantitation/detection limit (LLOQ) will be replaced by half of the LLOQ, data above the upper limit of quantification will be replaced by ULOQ value.

Quantitative analyses

For all laboratory variables, vital signs and ECG variables above, descriptive statistics for results and changes from baseline will be provided for each visit, the last value and the worst value (minimum and/or maximum value depending on the parameter) during the on-treatment period.

All laboratory parameters (except urinalysis parameters) and vital signs parameters (except weight and height) will be summarized using the analysis windows as defined in Table 12. Urinalysis, ECG and weight will be summarized by planned visit using central measurements only.

Analyses according to PCSA

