Potentially clinically significant abnormality (PCSA) analyses will be performed based on the PCSA list in effect at Sanofi at the time of the database lock. For parameters for which no PCSA criteria are defined, similar analyses will be done using the normal range, if applicable.

For parameters defined as efficacy endpoints, PCSA summaries will not be provided.

Analyses according to PCSA will be performed based on the worst value during the treatmentemergent period, using all measurements (either local or central, either scheduled, nonscheduled or repeated).

For laboratory variables, vital signs and ECG variables above, the incidence of participants with at least one PCSA during the treatment-emergent period will be summarized regardless of the baseline level and according to the following baseline status categories:

- Normal/missing
- Abnormal according to PCSA criterion or criteria

For ECG, the incidence of participants with at least one abnormal ECG during the treatmentemergent period will be summarized regardless of the baseline level and according to the following baseline status categories:

- Normal/missing
- Abnormal

Additional analyses for drug-induced liver injury

The following additional analyses will be performed for drug-induced liver injury:

- A graph of the distribution of peak values of ALT versus peak values of total bilirubin during the treatment-emergent period will be provided.
- For each liver function test (eg, ALT), participants having experienced a PCSA (eg, ALT >5 ULN) will be summarized using the following categories: Returned to baseline PCSA status (or returned to value \le ULN in case of missing baseline) before last IMP dose, Returned to baseline PCSA status after last IMP dose, Never returned to baseline PCSA status, No assessment after elevation. This summary will be performed by categories of elevation (ALT >3, >5, >10, >20 ULN).

The incidence of liver related AEs will be summarized by study intervention group. The selection of PT will be based on SMQ Hepatic disorder.

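### SAP version 2 drops the Stage 1 safety tables, so cumulative safety results for 8 mg (randomised in Stage 1 only) are not like for like with pooled placebo or 15 mg

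*SAP*

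**What the plan says.** The change table for SAP version 2 (Table 1) records, as one consequence of stopping the study, that "Safety populations and all safety analyses on Stage 1 populations are removed". Section 4.7 then sets the rule that remains: "All safety analyses will be performed on the Extended combined Stage 1 and Stage 2 safety population as defined in Section 3, unless otherwise specified". Table 4 defines that population as participants with screening eGFR 30 to 89.9 "who are randomized in Stage 1 or Stage 2 and who took at least 1 dose of study intervention", grouped by treatment received. Section 4.1 adds: "Unless otherwise specified, analyses will be performed by intervention group".

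SAP Section 1.1 shows how the arms differ. In Stage 1, "eligible participants, aged 18 to 50 years with an eGFR in (45 to 89.9) are randomized with a 1:1:1 ratio" to placebo, 8 mg or 15 mg. Stage 2 randomised 1:1 to placebo or 15 mg only, and admitted patients with eGFR down to 30 and, in that low-eGFR group, age up to 55.

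The affected outputs are cumulative:

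- **Adverse events (Section 4.7.2):** "The AE summaries of Table 7 will be generated with number (%) of participants experiencing at least one event".
- **PCSA (Section 4.7.3.1):** "the incidence of participants with at least one PCSA during the treatment-emergent period will be summarized regardless of the baseline level".
- **Laboratory, vital-sign and ECG variables (Section 4.7.3.1):** "descriptive statistics for results and changes from baseline will be provided for each visit, the last value and the worst value" during the on-treatment period.
- **Lens and depression (Sections 4.7.3.4 and 4.7.3.5):** new-onset lens findings, worst BDI-II category and BDI-II worsening, all as counts or percentages of participants.
- **Hospitalization (Section 4.8.5):** a combined-stage percentage, plus a Stage 1 percentage and a Kaplan-Meier analysis.

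The exception for analyses specified otherwise gives no relief: no Stage 1 adverse-event, PCSA, lens or BDI-II table is specified anywhere. Protocol Section 11.3.2 had defined a separate Stage 1 Safety population.

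**The concern.** A percentage with at least one event, or a worst value over follow-up, grows with time observed. Every 8 mg patient entered in Stage 1, while most of the placebo and 15 mg patients, at planned sizes, entered in Stage 2.

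Stage 2 follow-up is inferred to be shorter. Its only post-baseline MRI is at Month 18 (Protocol Section 9.4.1), and SAP Section 4.4.2.2 says none will be available. By the futility analysis, all Stage 1 patients had completed 9 months and about 30% had completed 18 months, or had discontinued (SAP Section 4.9.2).

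If hazards are equal and Stage 2 exposure is shorter, 8 mg will look worse than placebo and worse than 15 mg with no drug effect behind it. A true gradient from 8 mg to 15 mg could be hidden. A real harm of 15 mg would still show against pooled placebo, because those two arms were randomised in equal ratio within each stage.

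**Working it through.** **Planned sizes (SAP Section 2).** Stage 1 has 80 per arm in three arms; Stage 2 has 160 per arm with eGFR 45 to 89.9 and 40 per arm with eGFR 30 to 44.9. The total is 3×80 + 2×160 + 2×40 = 640, which agrees with the 640 in Protocol Section 9.4.14.1. The pooled safety groups are therefore:

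| Group | n | From Stage 2 | eGFR 30 to 44.9 |
|---|---|---|---|
| Placebo | 280 | 200 (71%) | 40 (14%) |
| 15 mg | 280 | 200 (71%) | 40 (14%) |
| 8 mg | 80 | 0 | 0 |

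**Model (assumed).** The documents give no exposure by stage, actual Stage 2 enrolment or hazards. Take the same constant hazard h in every arm, with mean exposure of 1.4 years in Stage 1 and 0.6 years in Stage 2. Then p = 1 − exp(−h × exposure); 8 mg shows p1, and placebo or 15 mg shows (80·p1 + n2·p2)/(80 + n2). Here n2 is 200, 100 or 50 per arm (100%, 50% or 25% of plan).

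At h = 0.3: p1 = 1 − exp(−0.42) = 34.3% and p2 = 1 − exp(−0.18) = 16.5%. With n2 = 200, the pooled value is (80×34.3 + 200×16.5)/280 = 21.6%.

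| h per year | n2 | 8 mg | Pooled | Difference (points) | In SE |
|---|---|---|---|---|---|
| 0.3 | 200 | 34.3% | 21.6% | 12.7 | 2.2 |
| 0.3 | 100 | 34.3% | 24.4% | 9.9 | 1.6 |
| 0.3 | 50 | 34.3% | 27.4% | 6.9 | 1.0 |
| 0.1 | 200 / 100 / 50 | 13.1% | 7.9 / 9.0 / 10.3% | 5.2 / 4.0 / 2.8 | 1.3 / 0.9 / 0.6 |
| 0.05 | 200 / 100 / 50 | 6.8% | 4.0 / 4.6 / 5.3% | 2.7 / 2.1 / 1.5 | 0.9 / 0.7 / 0.4 |

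The ratios at h = 0.3 are 1.59, 1.41 and 1.25. The SE is unpooled, for 80 against 80 + n2.

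**Range.** With Stage 1 exposure of 1.0, 1.2, 1.4 or 1.6 years, Stage 2 of 0.3, 0.6 or 0.9 years, h of 0.1, 0.3 or 1.0, and the three values of n2 (108 combinations), the ratio runs from 1.02 to 2.33. With equal exposure in both stages it is 1.00.

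**Low-eGFR hazard.** If the hazard is doubled or tripled in the 20% of Stage 2 with eGFR 30 to 44.9, the base-case ratio of 1.59 falls to 1.46 or 1.36. Over the same 108 combinations the minimum becomes 0.95 (9 below 1) or 0.86 (12 below 1).

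**Masking.** Solve for the 15 mg hazard at which the pooled 15 mg percentage equals the 8 mg percentage. At an 8 mg hazard of 0.3, a true 15 mg to 8 mg hazard ratio of 1.76, 1.52 or 1.32 (n2 = 200, 100, 50) would appear as equal percentages. If the placebo hazard is also 0.3, then at n2 = 200 the 15 mg column would still show 34.3% against 21.6% on placebo.

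**Worst values.** With independent visit noise and no drug effect, the expected maximum of 6 standard normals is 1.267 and of 3 is 0.846. Taking 6 visits in Stage 1 (to Month 15) and 3 in Stage 2 (to Month 6), the pooled mean is (80×1.267 + 200×0.846)/280 = 0.966. The 8 mg shift is 0.30 within-patient SD, or 0.16 at n2 = 50.

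**The case against.** The strongest reply is that the contrast that matters is intact. Only 15 mg went into Stage 2 and the extension, pooled 15 mg against placebo is undistorted, and the committee's dose review had already been done on Stage 1 data. Safety is descriptive with no testing, exposure and participant-years are tabulated (Section 4.7.1), many variables are also summarised by visit, and the reduction in analyses was a deliberate response to stopping. This limits the consequence. It does not make the 8 mg column comparable: tabulated exposure lets a reader see the imbalance but does not correct the percentages, and it leaves the eGFR and age differences untouched.

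The size is also assumed. Only one of the nine base-case results exceeds 2 SE, and at 0.05 per year all are below 1 SE. That is fair, and the figures are illustrative. The worst-value shift likewise rests on assumed visit counts and independent noise.

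The direction can reverse if low-eGFR patients carry a much higher hazard and the stage exposures are close. That is correct. It is a further sign that the columns differ in population as well as in time observed.

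Finally, for uncommon events Stage 1 tables trade bias for noise. At 0.05 per year the root-mean-square error for 8 mg against placebo is about 3.7 to 4.1 points pooled and 4.0 in Stage 1 alone. At 0.3 per year it is 14.0, 11.7 or 9.5 pooled (n2 = 200, 100, 50) against 7.5. The gain is therefore mainly for mid-frequency events, which is a reason to keep both sets of tables.

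**Conclusion.** The concern holds. Under SAP version 2, cumulative safety results for 8 mg are not comparable with placebo or 15 mg, and no stage-specific table replaces those removed, except for hospitalization. That follows from the design and needs no assumption beyond the two stages differing in follow-up or risk.

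The size does rest on assumptions. Under equal constant hazards the spurious ratio lies between 1.02 and 2.33 over the range examined, and it is smaller for early-onset events. By-visit summaries, the Stage 1 hospitalization percentage and the Kaplan-Meier analysis are largely protected. The change should be made, with medium confidence about how much it matters in the actual data.

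A separate and smaller point: SAP Section 2 still places patients with eGFR 30 to 44.9 outside the primary safety population, to be analysed separately, while Table 4 and Section 4.7 include them. They keep a by-visit eGFR summary (Section 4.3.2.4) but no safety display of their own, although Protocol Section 11.3.2 had planned a secondary safety population for them.

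**What to change.** - Keep the pooled tables for 15 mg against placebo.
- Add the key cumulative tables for Stage 1 alone, with its three concurrently randomised arms: TEAE, SAE, AESI, adverse events leading to discontinuation, PCSA, lens findings, worst BDI-II and BDI-II worsening, and worst values. Under equal hazards the expected ratio there is 1.00.
- Add first-event rates per 100 participant-years by arm as support. They assume a roughly constant hazard, so they do not replace the Stage 1 tables.
- For hospitalization, compare 8 mg using the Stage 1 percentage or the Kaplan-Meier analysis already planned.
- Add one short descriptive display (TEAE, SAE, AESI, adverse events leading to discontinuation, PCSA) for Stage 2 patients with eGFR 30 to 44.9, and align the Section 2 sentence with Table 4 and Section 4.7.

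The cost is rerunning existing table programs on Stage 1, one rate column, one short display and one edited sentence. Precision falls. At 10% incidence, SE = √(0.1×0.9×(1/n_a + 1/n_b)) is 4.7 points for 80 against 80, compared with 3.8 for 80 against 280. For the low-eGFR display it is 6.7 points at 40 against 40, and 9.5 or 13.4 if only 20 or 10 per arm were enrolled, so that display can only be descriptive.
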